2.3 Triple Negative Breast Cancer

Approximately 15-20% of all breast cancers do not express functional cell surface receptors like ER, PR, and HER2. Triple-negative tumors are typically associated with a higher histologic grade, increased mitotic count, pushing margins of invasion, and a stromal lymphocytic response. Patients with TNBC often have poorer prognosis compared to other breast cancer subtypes. It is commonly misconceived that TNBC is more sensitive to chemotherapy. Although higher pathologic complete response rate (pCR) was observed in TNBC (25–45%) compared to luminal breast cancers (6–7%), patients with TNBC had worse four-year distant disease free and overall survival⁷. It has been demonstrated in multiple studies that the loss of ER protein expression is a result of epigenetic changes in the tumors. Hypermethylation of the CpG islands within the ER α promoter has been observed in a significant fraction of breast cancers⁸. Moreover, HDAC1 has been reported to interact with and suppresses transcription activity of ER α . The interaction of HDAC1 with ER α is mediated by the activation function-2 (AF-2) domain and DNA-binding domain of ER α . Treatment of ER-negative breast cancer cells with TSA, an HDAC inhibitor, induced re-expression of ER α . These findings strongly suggest that HDAC1 affects breast cancer progression by promoting cellular proliferation in association with a reduction in both ER α protein expression and transcriptional activity. Therefore, HDAC1 may be a potential target for therapeutic intervention in the treatment of a subset of ER-negative breast cancers⁹.

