5.7 Duration of Follow Up

Patients will be followed for 30 days after the last dose of study medication or until death, whichever occurs first. In patients who receive other primary treatment after entinostat and anastrozole administration and prior to surgery, we will collect a summary of the treatment given to correlate, if needed, with tissue samples from the surgical procedure – no additional data will be collected after that time. Patients continuing to experience adverse events attributable to the study drug will be followed as needed until resolution or stabilization of the adverse events. Patients who either are found to be ineligible or refuse to start treatment after consenting will not be followed and their information will not be collected.

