5.8 Criteria for Removal from Study

Patients will be removed from study when any of the criteria listed below applies. The reason for study removal and the date the patient was removed must be documented in the case report form.

- Evidence of rapid disease progression during treatment at the discretion of the treating investigator.
- Non-compliance with the study protocol; including, but not limited to not attending the majority of scheduled visits. The Protocol Chair will determine when non-compliance should lead to removal from study.

Note: The patients will still be included in the overall evaluation of response (intent-to-treat analysis).

- Unacceptable major toxicity or the dosing delay and/or delay in the surgery ≥ 2 weeks.

Note: The patients will still be included in the overall evaluation of response (intent-to-treat analysis).

- Intercurrent illness or condition that would, in the judgment of the treating investigator, affect assessment of clinical status to a significant degree or require discontinuation of study treatment.
- At subject's own request.

Note: The reason for discontinuation from the study must be documented. The patients will be included in the overall evaluation of response (intent-to-treat analysis) if any protocol therapy was administered prior to withdrawal.

- Study is closed for any reason (e.g. new information shows that the patient's welfare would be at risk if she continued study treatment).
- Subject withdraws consent for follow-up.
- Subject is lost to follow-up.
- Study is terminated for any reason.

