9.1.1 Collections

In the first cohort:

Tumor tissue samples from the following time points will be obtained:

1. Prior to starting treatment or tissue sample at the original diagnostic procedure. (T0)
2. At the time of definitive surgery (i.e., mastectomy or lumpectomy). A separate tumor biopsy is not needed on the day of surgery; tissue will be taken from the surgical specimen. (T1)

Note: If a subject receives additional preoperative treatment after discontinuing study treatment and prior to surgery, every attempt should be made to collect a tissue sample for the study prior to initiation of the new treatment; in these cases, tissue will still be collected at the time of definitive surgery, as above.

Every effort should be made to provide a core specimen from the surgical sample after treatment. The site pathologist should remove a core samples during the dissection of the surgical specimen (using a 5-mm skin punch biopsy device). The samples should be processed preferably within 1 hour, but may be processed up to 2 hours of removal from the patients. This core specimen should be fixed in formalin and processed separately as per the American Society of Clinical Oncology/College of American Pathologists Guideline Recommendations published in Journal of Clinical Oncology 2010⁴².

In the second cohort:

Approximately six core biopsy specimens will be obtained with each biopsy. Alternative to core needle biopsy, fine needle aspirate (FNA) is allowed in this cohort of patients. Cytology cell blocks should be made from FNA specimens using routine institutional cytology protocol. Biopsy should be obtained from soft tissue metastasis such as breast, liver, skin, lung, or intra-abdominal implants. Bone biopsy, paracentesis (ascites), and thoracocentesis (pleural effusion) specimens are not adequate.

Tumor tissue samples from the following time points will be obtained:

1. Pretreatment biopsy (biopsy#1) will be performed within 3 weeks after registration. However, the pretreatment biopsy can be omitted in patients who have recent biopsy but have not been started on breast cancer treatment within 12 weeks prior to the registration and there is adequate tumor tissue sample as per section 3.1.9. (T0-Second cohort)

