11.1.2 Pathologic Response

- Pathologic Complete Response (pCR): No viable invasive cancer in pathologic specimen, as determined by histological examination. We will report whether in situ disease only was present in the specimen versus no disease. We will also report for each woman whether she had a pCR in the breast only, in the lymph nodes only, or in both.
- Nodal Disease: We will report the number of women who had positive lymph node prior to starting study drugs, or at the time of surgery: 0, 1-3, 4-10, or >10 lymph nodes.

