12. STATISTICAL CONSIDERATIONS

12.1 Study Design/Endpoints

This is a Pilot and Phase II, single-arm, open-labeled, multi-center study of entinostat in combination with anastrozole/tamoxifen in women with triple negative breast cancer. The main objective of this study is to assess the safety and efficacy of the combination of entinostat and anastrozole/tamoxifen. The primary endpoints, that we will use to evaluate the efficacy of the entinostat and anastrozole/tamoxifen, are the reduction in proliferative index (Ki67) and upregulation of ER after treatment with entinostat and anastrozole/tamoxifen therapy. We define patient's response as at least 50% reduction in the Ki67 index AND greater than 1% ER-positivity OR pathologic complete response in the post-treatment surgical specimens. For the evaluation of these biological endpoints, the analysis will include ALL of the patients in both cohorts (the first cohort-operable stage I-II and the second cohort-unresectable locally advanced/metastatic) as well as both anastrozole and tamoxifen groups.

In the pilot phase, the classic cohort-of-3-study design will be used. The primary endpoint of this part of the study is to determine the recommended dose for the phase II part as well as to evaluate the safety of both combinations. The dose levels are defined below for both pre- and postmenopausal groups. For safety, each combination (entinostat and anastrozole as well as entinostat and tamoxifen) will be evaluated separately. For both groups (anastrozole and tamoxifen), the first cohort of 3 patients will be treated starting at dose level 1 (d_1). If ≤ 1 patient experiences DLT, an additional 3 patients will be treated at this dose level (d_1). If ≥ 2 patients in the initial cohort of 6 patients suffer DLT, then up to 6 additional patients will be enrolled at the dose level -1. The phase II part will continue with the highest dose level with < 2 out of 6 patients experiencing a DLT. Therefore, we will need 6-12 patients for each combination

in this part of the study. The 6 patients from the pilot phase of each combination that are treated with the recommended dose level for the phase II will be included in the primary endpoint analysis.

The dose modification schemas are as follow for both postmenopausal and premenopausal women:

Dose Modification Schema for Postmenopausal Women		
Dose Level	Dose	
	Entinostat (mg)	Anastrozole (mg) daily
-1	3 mg weekly (on day 1, 8, 15, 22, and 29)	1

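### In the first cohort, nothing stops a pathologic complete response after non-protocol preoperative treatment from counting as a study response, and no rule says which specimen decides

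*Combined protocol and SAP*

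**What the plan says.** - **Responder definition (Section 12.1).** Response is "at least 50% reduction in the Ki67 index AND greater than 1% ER-positivity OR pathologic complete response in the post-treatment surgical specimens". The last alternative, "OR pathologic complete response in the post-treatment surgical specimens", is enough without the other two. Section 11.1.2 defines pCR as "No viable invasive cancer in pathologic specimen, as determined by histological examination". Neither mentions treatment given between study drug and surgery.
- **Other treatment before surgery is foreseen.** Section 5.7: "In patients who receive other primary treatment after entinostat and anastrozole administration and prior to surgery, we will collect a summary of the treatment given". The stated use of that summary is correlation with the surgical tissue, if needed.
- **Tissue in these patients (Section 9.1.1).** "If a subject receives additional preoperative treatment after discontinuing study treatment and prior to surgery, every attempt should be made to collect a tissue sample" before the new treatment starts, but "in these cases, tissue will still be collected at the time of definitive surgery, as above". Surgical tissue is the specimen labelled T1 for the first cohort.
- **Analysis set.** Under Section 5.8, for removal because of non-compliance, or because of toxicity or delay: "The patients will still be included in the overall evaluation of response (intent-to-treat analysis)". Removal at the patient's own request has a similar note, provided some protocol therapy was given. Section 12.1 says the biological endpoints are analysed in all patients of both cohorts.
- **Decision rule (Section 12.1).** Stop if none of the first 12 respond; otherwise add 20, and call the combination promising if at least 4 of 32 respond. The stated probabilities are 0.87 for power at 20%, 0.07 for a false positive at 5%, and 0.54 and 0.07 for early stopping at 5% and 20%.

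**The concern.** Consider a first-cohort patient who stops study drug for toxicity, is given other preoperative treatment and has no invasive cancer left at surgery. She stays in the response evaluation, her surgical specimen is collected in the usual way, and that specimen shows a pCR. On the text as it stands she is a responder to entinostat plus endocrine therapy, although the study treatment was abandoned.

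The trial has no control arm to absorb this, and its thresholds are low: one response carries it past stage 1, and four in 32 decide the result. A single misattributed response therefore matters. If the question is left open until such a patient appears, it will be settled in an open-label trial with her result already known.

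**Working it through.** **1. Does any section close the gap?** I read the responder definition as (Ki67 and ER) or pCR. That is the workable reading, because a specimen with no invasive tumour gives no post-treatment Ki67 value.

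| Question | Where | Answer |
|---|---|---|
| Can other treatment precede surgery? | 5.7, 9.1.1 | Yes, foreseen |
| Is tissue required before it starts? | 9.1.1 | No, best effort |
| Is surgical tissue still taken? | 9.1.1 | Yes |
| Does the patient stay in the evaluation? | 5.8 | Yes, for the three removal reasons above |
| Is pCR conditional on no other therapy? | 11.1.2, 12.1 | No |
| Is one specimen named as decisive? | 9.1.1, 11.1.1, 12.1 | No |

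An earlier sample does not block the pCR route: a pCR at surgery satisfies that branch whatever the earlier sample showed.

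**2. Reproduce the plan's figures.** With X1 ~ Bin(12, p) and X2 ~ Bin(20, p):

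- P(stop) = (1 − p)^12, which is 0.95^12 = 0.540 and 0.80^12 = 0.069.
- P(promising) = Σ over x = 1…12 of P(X1 = x) · P(X2 ≥ 4 − x).
- At p = 0.05: x = 1 gives 0.3413 × 0.0755 = 0.0258; x = 2 gives 0.0988 × 0.2642 = 0.0261; x = 3 gives 0.0173 × 0.6415 = 0.0111; x ≥ 4 gives 0.0022. The sum is 0.065.
- At p = 0.20 the same sum is 0.866.

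These agree with the stated 0.54, 0.07, 0.07 and 0.87.

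**3. Illustrate the gap.** Inputs: the true study response rate is 5%. A switcher is scored as a responder with probability c = 0.25 or 0.45, the pCR range that Section 2.3 gives for triple negative disease when discussing chemotherapy sensitivity. The number of switchers is assumed, because the documents give none.

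For one switcher, P(promising) = (1 − c)·A + c·B, where A and B are the probabilities given that she is scored a non-responder or a responder.

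- In stage 1, A = 0.058 and B = 0.201. So 0.75 × 0.058 + 0.25 × 0.201 = 0.094, and 0.55 × 0.058 + 0.45 × 0.201 = 0.122. Stopping becomes 0.95^11 × (1 − c), which is 0.5688 × 0.75 = 0.427 or 0.5688 × 0.55 = 0.313.
- In stage 2, A = 0.060 and B = 0.165, giving 0.086 and 0.107.

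| Switchers (stage 1, stage 2) | False promising, c = 0.25 to 0.45 | Early stopping |
|---|---|---|
| 0, 0 | 0.065 | 0.54 |
| 1, 0 | 0.094–0.122 | 0.43–0.31 |
| 0, 1 | 0.086–0.107 | 0.54 |
| 1, 1 | 0.121–0.190 | 0.43–0.31 |

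**4. Cost of counting switchers as non-responders.** Set c = 0 and repeat the two-stage sum.

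| Affected (stage 1, stage 2) | Power at 20% | Type I error at 5% |
|---|---|---|
| 0, 0 | 0.866 | 0.065 |
| 1, 0 | 0.842 | 0.058 |
| 0, 1 | 0.856 | 0.060 |
| 1, 1 | 0.831 | 0.053 |
| 1, 2 | 0.817 | 0.049 |

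**The case against.** The strongest reply is that no sentence says a response after other treatment counts. Section 12.1 describes the endpoints as changes after entinostat and endocrine therapy, and Section 1.2 speaks of response to the preoperative combination. The request for tissue before the new treatment has little purpose unless that sample is the one of interest, and the treatment summary allows affected specimens to be identified. Section 12.1 also allows about 10% inevaluable patients. All of this shows intent, and it partly protects the Ki67/ER route. It is not a rule: the early sample is neither required nor named as decisive, inevaluable is not defined, and pCR has no safeguard.

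A reader might be tempted to go further. The documents do not support these steps:

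- **That the plan deliberately credits chemotherapy responses.** The crediting follows from silence plus the intent-to-treat notes. The treatment is called other primary or additional preoperative treatment. Chemotherapy is a natural inference from Section 2, but Section 5.6.1 recommends it after surgery.
- **That Section 5.8 keeps patients who progress rapidly.** Its intent-to-treat note is not attached to that reason for removal. They would enter only through the all-patients wording in Section 12.1. Nothing in the documents says who is likely to switch.
- **That both cohorts and both response routes are equally exposed.** The second cohort has no planned definitive surgery, so pCR at surgery is essentially a first-cohort matter. The Ki67/ER route also needs ER re-expression, and nothing here shows that other treatment produces it; I have not quantified it.
- **That the stated error rates are wrong.** They reproduce.

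**Conclusion.** The gap is real but narrow. A first-cohort patient with a pCR after non-protocol preoperative treatment meets the responder definition as written, and the plan does not say which specimen decides response. One such patient could raise the false-positive probability from 0.065 to roughly 0.09–0.12, depending on stage and pCR rate. In stage 1 she would lower the chance of correctly stopping from 0.54 to 0.43–0.31. These figures illustrate and do not predict: they assume the number of switchers, that the other treatment is effective enough to reach the Section 2.3 pCR range, and a true study response rate of 5%. If nobody switches, nothing changes. This should be fixed because the decision thresholds are low and the remedy is cheap.

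**What to change.** Add one rule to Sections 11.1.1, 11.1.2 and 12.1: response, whether by Ki67/ER or by pCR, is scored only on tissue obtained before any non-protocol anticancer treatment. A patient without such tissue counts as a non-responder in the two-stage rule and is left out of the paired Ki67/ER change analysis. In Section 9.1.1, give surgical tissue taken after other treatment a label distinct from T1 and keep it for descriptive use.

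This needs wording and a specimen label, and no new procedure. It has a price in power at a 20% true rate: from 0.87 to about 0.84–0.86 with one patient lacking usable tissue, and about 0.82 with three (one in stage 1, two in stage 2). Type I error stays at or below 0.065. The paired analysis loses the same patients, so their number should be reported.

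Treating them as inevaluable within the 10% allowance is the alternative. It would remove patients who stopped study treatment from the denominator, which sits badly with the intent-to-treat notes in Section 5.8. Whichever is chosen should be written down before any such specimen is read.

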12.2 Sample Size/Accrual Rate

For the pilot phase, the study will require 12-24 patients to complete, allowing for 3-6 patients per dose level and 2 predefined dose levels for 2 combination treatments (entinostat and anastrozole as well as entinostat and tamoxifen). In the phase II period, the study will require 12-35 patients to complete. However, we will include the 12 patients in the pilot phase that are treated with the recommended dose level of each combination for phase II in the primary endpoint analysis. Therefore, the total sample size for this study is 12-41 patients. At an anticipated accrual rate of 15-20 patients/year, we anticipate that the phase II part will need to accrue patients for anywhere from 7 to 33 months.

NOTE: The maximum total sample size will most likely remain 41 patients. The only situation that this trial will require additional 6 patients is that there are ≥ 2 patients in the first cohort of 6 patients suffer DLT in dose level 1 in both combination treatments. As of November 2011, there were 3 patients enrolled in the pilot phase of this study. There is no DLT observed in this first 3 patients treated with entinostat and anastrozole. Furthermore, a phase II study of

entinostat and AIs including anastrozole was recently completed which demonstrated that this combination is safe and tolerable with the majority of AEs being only grade 1 or 2⁴⁷. Taken this together, it is highly unlikely that there will be ≥ 2 patients in the first cohort of 6 patients suffer DLT in dose level 1 in entinostat and anastrozole group.

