3.3 Inclusion of Minorities

Women of all races and ethnic groups are eligible for this trial.

Accrual Targets			
Ethnic Category	Sex/Gender		
	Females	Males	Total
Hispanic or Latino	10	+ 0	= 10
Not Hispanic or Latino	35	+ 0	= 35
Ethnic Category: Total of all subjects	45 (A1)	+ 0 (B1)	= 45 (C1)
Racial Category			
American Indian or Alaskan Native	5	+ 0	= 5
Asian	5	+ 0	= 5
Black or African American	5	+ 0	= 5
Native Hawaiian or other Pacific Islander	5	+ 0	= 5
White	25	+ 0	= 25
Racial Category: Total of all subjects	45 (A2)	+ 0 (B2)	= 45 (C2)

Accrual Rate: 2-3 pts/month Total Expected Accrual: 12 Min 45 Max

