Dose Modification Schema for Premenopausal Women		
Dose Level	Dose	
	Entinostat (mg)	Tamoxifen (mg) daily
-1	3 mg weekly (on day 1, 8, 15, 22, and 29)	20
1	5 mg weekly (on day 1, 8, 15, 22, and 29)	20

Therefore, the total number of patients for the pilot phase of the study will be 6-12 for each treatment groups (entinostat and anastrozole as well as entinostat and tamoxifen) or the total of 12-24 patients.

The phase II part will continue with the dose level in which there is ≤ 1 out of 6 patients experiencing a DLT. However, if there are ≥ 2 out of 6 patients experiencing DLT at dose level -1, the study will be terminated due to toxicity.

The patients in the pilot phase will be included in the overall evaluation of response.

Toxicity will be graded according to the active version of National Cancer Institute (NCI)-Common Terminology Criteria for Adverse Events (CTCAE) as per section 7.3. Patients in both cohorts (the first cohort-operable stage I-II and the second cohort-unresectable locally advance/metastatic) in the pilot phase will be used to evaluate for DLT. In the second cohort, only adverse events (AEs) that occur during the first 29 day will be considered for DLT. DLT is defined as one or more of the following treatment-related:

1. Hematologic AEs
 - a. Absolute neutrophil count (ANC) $< 500/\text{mm}^3$ regardless of duration
 - b. Failure of ANC to recover $\geq 1,000/\text{mm}^3$ within 14 days
 - c. Grade ≥ 4 thrombocytopenia regardless of duration or grade 3 thrombocytopenia with significant bleeding.
 - d. Failure of platelet to recover $\geq 50,000/\text{mm}^3$ within 14 days
 - e. Hemoglobin < 6.5 g/dL despite transfusion lasting > 7 days
2. Grade ≥ 3 nonhematologic AEs (except for fatigue, diarrhea, and nausea/vomiting if manageable).
3. Grade ≥ 3 diarrhea lasting > 2 days despite being treated with optimal medical therapy, or associated with fever or severe dehydration.
4. Grade ≥ 3 fatigue lasting > 7 consecutive days.

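### The maximum sample size is given as 41 in the schema and 12.2 and as 45 in 3.3, while the components in 12.2 give an upper bound of 47

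*Combined protocol and SAP*

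**What the plan says.** The plan builds its total from three components in section 12.2:

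- Pilot: "For the pilot phase, the study will require 12-24 patients to complete". Section 5.2.1 agrees: "the total number of patients for the pilot phase of the study will be 6-12 for each treatment groups", "or the total of 12-24 patients".
- Phase II: "In the phase II period, the study will require 12-35 patients to complete". Section 12.1 explains the 35 as 32 patients (12 in stage 1, 20 in stage 2) plus about 10% for inevaluability.
- Overlap: "we will include the 12 patients in the pilot phase that are treated with the recommended dose level of each combination for phase II".

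Section 12.2 then draws the total: "Therefore, the total sample size for this study is 12-41 patients". The schema gives the same range. Section 3.3 gives "Total Expected Accrual: 12 Min 45 Max", and its ethnic and racial tables both sum to 45.

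The NOTE in 12.2 calls 41 the most likely maximum and names one exception: "The only situation that this trial will require additional 6 patients" is when at least two of the first six patients have a DLT at level 1 in both combinations. It also reports that, as of November 2011, three patients had been treated with entinostat and anastrozole without a DLT. The figure 47 is not written anywhere.

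The two descriptions of the pilot differ on the trigger. Section 5.2.1 de-escalates on one or more DLTs at level 1, and adds the second three patients only if the first three have none. Section 12.1 adds the second three if at most one of the first three has a DLT, and de-escalates on two or more of six.

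**The concern.** A protocol should have one upper limit on enrolment, and it should follow from the plan's own components. This one prints two limits, and neither equals the sum of the maxima in 12.2. The 41 is the total for an intermediate scenario, set down as the end of the range. The 45 is unexplained.

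At stake is the size of phase II after de-escalation. Only pilot patients treated at the recommended dose count toward the primary analysis (12.1), so those treated at level 1 in a combination that de-escalates must be replaced. If a printed limit were enforced when both combinations de-escalate, there might be too few recommended-dose patients for the 32-patient two-stage design.

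**Working it through.** **1. Totals.** Total = pilot + phase II accrual - pilot patients counted in phase II. With six patients treated at level 1 before any de-escalation:

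- no combination de-escalates: 12 + 35 - 12 = 35
- one de-escalates: 18 + 35 - 12 = 41 (the plan's figure)
- both de-escalate: 24 + 35 - 12 = 47 (also the NOTE's 41 + 6)

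If a combination de-escalates after only three patients, it adds 3 rather than 6 to the base of 35. That gives 38 (one, after three), 41 (both after three) or 44 (one after three, one after six). The possible totals are therefore 35, 38, 41, 44 and 47. The figure 45 is not among them.

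**2. Accrual time.** The plan states 7 to 33 months at 15-20 patients a year. This reproduces as 12/20 × 12 = 7.2 and 41/15 × 12 = 32.8. At 47 the longest time is 47/15 × 12 = 37.6 months.

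**3. Two-stage design.** Stop if there are 0 responses in 12; promising if there are at least 4 in 32. Exact binomial results, with the plan's figures in brackets: early stopping 0.540 at a 5% response rate (0.54) and 0.069 at 20% (0.07); type I error 0.065 (0.07); power 0.866 (0.87).

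**4. Effect of a cap if both combinations de-escalate after six patients each.** Twelve level-1 patients do not count.

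- Cap 41: 41 - 12 = 29 at the recommended dose; 29 × 0.9 ≈ 26 evaluable; power with the cut-off of 4 kept = 0.77.
- Cap 45: 45 - 12 = 33; 33 × 0.9 ≈ 30 evaluable; power = 0.84.
- No cap (47): 47 - 12 = 35, as planned.

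At a total of 44, nine level-1 patients do not count. A cap of 41 would then leave 41 - 9 = 32, and a cap of 45 would not bind.

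**5. How likely.** The documents give no DLT rate for either combination, so d = 10, 20 and 30% are assumed, equal in both. The calculation conditions on 0 of 3 DLTs with anastrozole and takes patients in full groups of three.

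*12.1 rule, both de-escalate:* P(at least 2 of the next 3, anastrozole) × P(at least 2 of 6, tamoxifen).

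- 10%: 0.028 × 0.114 = 0.003
- 20%: 0.104 × 0.345 = 0.036
- 30%: 0.216 × 0.580 = 0.125

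These are upper limits for reaching 47 under that rule, because they include tamoxifen patients having two DLTs among the first three.

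*5.2.1 rule, total of 47:* let a = 1 - (1 - d)³. Anastrozole must have a DLT in its next three, and tamoxifen none in its first three but at least one in its next three: a × (1 - d)³ × a.

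- 10%: 0.271 × 0.729 × 0.271 = 0.054
- 20%: 0.488 × 0.512 × 0.488 = 0.122
- 30%: 0.657 × 0.343 × 0.657 = 0.148

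Under the same rule and conditioning, both combinations de-escalate at all (total 44 or 47) with probability a × [1 - (1 - d)⁶] = 0.127, 0.360 and 0.580.

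**The case against.** The best defence is that the plan has already disclosed the exception. The NOTE says 41 is the likely maximum and provides for six more patients in a named situation, so 47 is implied. It also argues that the situation is remote. Under the rule the NOTE uses, and at a 10% DLT rate, the figure of about 3 in 1,000 bears that out. With none or one combination de-escalating, 41 is enough.

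Most of this stands, and it limits the consequence. A reader might infer that accrual will end at 41 or 45 and that the stated power is then lost. The documents do not support this: no section stops accrual at either number, the stopping rules concern toxicity and zero responses in 12, and the NOTE expressly lets enrolment pass 41. Even a strict limit of 45 would cost little power (0.84 against 0.87).

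A reader might also take the chance that both combinations de-escalate under 5.2.1 (0.22 at a 10% DLT rate, before conditioning on the three anastrozole patients) as the chance of needing 47. It is not, because that rule can de-escalate after three patients. The unconditional chance of 47 is (0.729 × 0.271)² = 0.039, and 0.054 given the 0 of 3.

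What the defence does not reach is the text itself. The NOTE leaves the range, the schema and the accrual time unchanged, and it does not explain 45. One could guess at 41 plus 10% (45.1), but 12.1 already puts the inevaluability allowance into the 35, and no section takes that step. The NOTE's reassurance is also argued only for anastrozole; section 2.4 says there is no earlier trial of entinostat with tamoxifen.

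**Conclusion.** The point holds as an inconsistency in a stated sample-size figure. The plan gives 41 and 45, its components give an upper bound of 47, and the NOTE concedes 47 without writing it. The two-stage boundaries, the stated operating characteristics and the expected enrolment are unaffected.

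The practical risk is conditional and modest. It needs both combinations to de-escalate, with the full shortfall only when each has treated six patients at level 1, and it needs someone to enforce a printed figure as a cap despite the NOTE.

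The probabilities rest on the assumed DLT rates, equal and independent across combinations. The powers assume 10% inevaluability, a 20% response rate and the cut-off of 4 kept. The 47 covers DLT-driven de-escalation only; the separate de-escalation for surgical delay in 12.3 is not budgeted in any total. The 38 months uses the 15-20 patients a year of 12.2; section 3.3 quotes 2-3 a month.

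**What to change.** - State one range, 12-47, in the schema, 3.3 and 12.2.
- In 12.2, describe 41 as the expected maximum when one combination de-escalates after six patients, and write out 47 where the NOTE now says six more.
- Make the ethnic and racial totals in 3.3 agree with the chosen maximum.
- Change the longest accrual time from 33 to about 38 months at 15 patients a year.
- Reconcile the de-escalation triggers in 5.2.1 and 12.1. The number treated at level 1 before de-escalation, and so the intermediate totals of 38 and 44, depend on them. A simple 35/41/47 list by number of combinations de-escalated should not be written in until that is done, since it holds only if six patients are always treated first.

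Apart from reconciling the triggers, the cost is wording and one table. The design and the expected enrolment do not change.
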